5.4. Withdrawal/Stopping Criteria

The following actions must be taken in relation to a subject who fails to attend the clinical unit for a required study visit:

- The site must attempt to contact the subject and re-schedule the missed visit as soon as possible.
- The site must counsel the subject on the importance of maintaining the assigned visit schedule and ascertain whether or not the subject wishes to and/or should continue in the study.
- In cases where the subject is deemed ‘lost to follow up’, the investigator or designee must make every effort to regain contact with the subject (where possible, 3 telephone calls and if necessary a certified letter to the subject’s last known mailing address or local equivalent methods). These contact attempts should be documented in the subject’s medical record.
- Should the subject continue to be unreachable, only then will he/she be considered to have withdrawn from the study with a primary reason of “lost to follow up”.

A subject may withdraw from study treatment at any time at his/her own request, or may be withdrawn at any time at the discretion of the investigator for safety, behavioral, or administrative reasons. If a subject withdraws from the study, he/she may request destruction of any samples taken, and the investigator must document this in the site study records.

This protocol defines several clinical laboratory values, 12-lead ECG values, vital sign values, and additional safety criteria that, if observed and confirmed, mandate cessation of drug dosing and further evaluations. Any laboratory result that meets the stopping criteria should be repeated once to confirm the value before the subject is withdrawn from the study.

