5.4.3. Renal Stopping Criteria

Study treatment will be discontinued for a subject who meets any of the following criteria:

- Persistent (confirmed on recheck) elevation of serum creatinine (>0.3 mg/dL) without an alternative cause identified
- Albumin to creatinine ratio ≥ 0.03 mg/mg
- New blood in urinalysis confirmed by microscopy without an alternative cause identified

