9.4. Key Elements of Analysis Plan

9.4.1. Primary Analyses

Safety Analyses

The following safety evaluations will be performed:

- Monitoring for AEs
- Routine clinical laboratory tests including chemistry, hematology, and urinalysis
- Vital signs
- Twelve-lead ECG readings
- Continuous cardiac monitoring (dual-lead telemetry)

Safety endpoints will include AEs, clinical laboratory test results (chemistry [including liver function parameters], hematology, and urinalysis), vital signs (BP, heart rate, respiratory rate, and body temperature), and 12-lead ECG readings.

All safety data will be presented in data listings. Subject demographics, medical history, and prior and concomitant medications will be summarized for each dose level using descriptive statistics. For continuous variables, these summaries will include number of subjects, mean, median, standard deviation, minimum, and maximum.

For categorical variables, the summaries will include frequencies and corresponding percentages. No inferential hypothesis testing will be performed on the safety variables.

Adverse events will be coded using the MedDRA classification system.

Treatment-emergent AEs will be defined as any AEs, regardless of relationship to study drug, that occur after the dose of study drug until the Follow-up visit. The treatment-emergent AEs will be summarized for each dose level at AE onset for the overall number of AEs and percentage of subjects who experience them. The total number of AEs will be summarized by dose level and overall. The AEs will be further summarized by severity and relationship to the study drug. If relationship information is missing, the AE will be considered treatment related. Listings for the subsets of SAEs

and treatment-related SAEs will be provided. The SAEs and number of AEs leading to discontinuation will be summarized. The incidence of AEs will also be summarized by system organ class and preferred term.

Clinical laboratory test results, vital signs, and 12-lead ECG results will be summarized by actual values and change from baseline. Clinical laboratory values that are outside of the reference ranges will be flagged and evaluated for clinical significance by the investigator. Any 12-lead ECG abnormalities will be summarized by each dose level. Physical examination findings and cardiac telemetry results will be listed.

Detailed descriptions of the analyses in this study will be presented in the RAP.

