
 
To investigate the safety and tolerability of GSK3342830 after administration of repeat IV doses in healthy adult subjects
 
	
 
Clinical safety data from AEs, clinical laboratory tests, vital signs (blood pressure, heart rate, temperature, and respiration rate), and 12-lead ECG readings
 

Secondary Objectives	Secondary Endpoints

 
To determine the pharmacokinetics of GSK3342830 after administration of repeat IV doses in healthy adult subjects
 
	
 
Plasma and urine concentrations and PK endpoints include AUC(0-t) and AUC(0-∞) on Day 1 only, AUC(0-τ), Cmax, Tmax, CL, Vss, t1/2, Cτ, Feu(t1- t2), Ae, and CLr of GSK3342830, as data permit
 

 
To assess dose proportionality of GSK3342830 after administration of repeat IV doses in healthy adult subjects
 
	
 
Pharmacokinetic endpoints include AUC(0-τ) and Cmax of GSK3342830 after administration of repeat IV doses for the assessment of dose proportionality, as data permit
 

Objectives	Endpoints

 
To examine the extent of accumulation, time invariance, and achievement of steady-state of GSK3342830 after administration of repeat IV doses in healthy adult subjects
 
	
 
Observed accumulation ratio (Ro) based on AUC and Cmax of GSK3342830 after administration of repeat IV doses, as data permit
 
Steady-state ratio (Rss) of GSK3342830 to assess time invariance, as data permit
 
Trough plasma concentrations at the end of the dosing interval (Cτ) to assess the achievement of steady-state of GSK3342830 after administration of repeat IV doses, as data permit
 

Exploratory Objectives	Exploratory Endpoints

 
To correlate PK parameters (AUC[0-t], AUC[0-∞], AUC[0-τ], and Cmax) of GSK3342830 with safety findings in healthy adult subjects after administration of repeat IV doses
 
	
 
Exposure-response analyses, as data permit
 

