
 
• Reporting for tables, figures and formal statistical analyses :             
 
• Planned time relative to dosing will be used in figures, summaries, statistical analyses and calculation of any derived parameters, unless otherwise stated.
 
• The impact of any major deviation from the planned assessment times and/or scheduled visit days on the analyses and interpretation of the results will be assessed as appropriate.
 
 
 
• Reporting for Data Listings:             
 
• Planned and actual time relative to study drug dosing will be shown in listings (Refer to IDSL Statistical Principle 5.05.1).
 
• Unscheduled or unplanned readings will be presented within the subject's listings.
 
• Visits outside the protocol defined time-windows (i.e. recorded as protocol deviations) will be included in listings but omitted from figures, summaries and statistical analyses.
 
 
 
	
Unscheduled Visits	

 
• Unscheduled visits will not be included in summary tables.
 
• Unscheduled visits will not be included in figures.
 
• All unscheduled visits will be included in listings.
 
	
Descriptive Summary Statistics	
Continuous Data	Refer to IDSL Statistical Principle 6.06.1
Categorical Data	N, n, frequency, %
Reporting of Pharmacokinetic Concentration Data	
Descriptive Summary Statistics	Refer to IDSL Statistical Principle 6.06.1 Assign zero to NQ values (Refer to GUI_51487 for further details)
Reporting of Pharmacokinetic Parameters	
Descriptive Summary Statistics (Log Transformed)	N, n, geometric mean, 95% CI of geometric mean, standard deviation (SD) of logged data and between geometric coefficient of variation (CV b - (%)) will be reported. $CV_b (\%) = \sqrt{(\exp(SD^2) - 1) * 100}$ (SD = SD of log transformed data)

Reporting Standards	
Parameters Not Being Log Transformed	Tmax, %AUCex, tlast, lambda_z, lambda_z_lower, lambda_z_upper, lambda_z_no. of points, Ratio of time invariance, Ratio of accumulation, Feu(t1-t2), CLr, Ae
Listings	Include all following PK parameters: Cmax, AUC0-∞, AUC0-t, AUC(0-τ), t1/2, CL, Vss, Cτ, Ratio of time invariance, Ratio of accumulation, Tmax, %AUCex, tlast, lambda_z, lambda_z_lower, lambda_z_upper, lambda_z_no. of points, Feu(t1-t2), CLr, Ae.
Graphical Displays	

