**10.4.1. General**

Multiple Measurements at One Time Point

 
• Mean of the measurements will be calculated and used in any derivation of summary statistics but if listed, all data will be presented.
 
• If there are two values within a time window the value closest to the target day for that window will be used. If values are the same distance from the target then the mean will be taken.
 
• Subjects having both High and Low values for Normal Ranges at any post-baseline visits for safety parameters will be counted in both the High and Low categories of “Any visit post-baseline” row of related summary tables. This will also be applicable to relevant Potential Clinical Importance summary tables.
 

Study Day

 
• Calculated as the number of days from treatment date :             
 
• Ref Date = Missing → Study Day = Missing
 
• Ref Date < Treatment Date → Study Day = Ref Date – Treatment Date
 
• Ref Date ≥ Treatment Date → Study Day = Ref Date – (Treatment Date) + 1
 
 
 

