## 10.5. Appendix 5: Premature Withdrawals and Handling of Missing Data

### 10.5.1. Premature Withdrawals

Element	Reporting Detail
General	
 
• Subject study completion (i.e. as specified in the protocol) was defined as one who has completed all phases of the study including the follow-up visit.
 
• Withdrawn subjects may be replaced in the study.
 
• All available data from subjects who were withdrawn from the study will be listed and all available planned data will be included in summary tables and figures, unless otherwise specified.
 

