Lab Test	Treatment	N	Planned Relative Time	n	Mean	SD	Median	Min.	Max.
XXXXXXXX (XXX)	GSK3342830 250 mg	XXX	Baseline	xx	xx.x	xx.xx	xx	xx	xx
			Day 2	xx	xx.x	xx.xx	xx	xx	xx
			Follow-Up	xx	xx.x	xx.xx	xx	xx	xx
	GSK3342830 500 mg	XXX	Baseline	xx	xx.x	xx.xx	xx	xx	xx
			Day 2	xx	xx.x	xx.xx	xx	xx	xx
			Follow-Up	xx	xx.x	xx.xx	xx	xx	xx
	...	XXX	Baseline	xx	xx.x	xx.xx	xx	xx	xx
			Day 2	xx	xx.x	xx.xx	xx	xx	xx
			Follow-Up	xx	xx.x	xx.xx	xx	xx	xx

*Note to programmer: Continue for all treatments in Part 1, Part 2, and Part 3. Present Part 2 and Part 3 on separate pages. Timepoints for Part 1 and Part 3 are Baseline, Day 2, Follow-Up. Timepoints for Part 2 are Baseline, Day 2, Day 5, Day 10, Day 15, and Follow-Up.*

Note: For subjects Baseline is defined as the last nonmissing measurement before dosing.  
 Unscheduled measurements are not included in this summary table except when calculating baseline.

GlaxoSmithKline

Example : LB1  
Protocol : 204847  
Population : Safety

Page 1 of n

Table 2.7

Summary of Clinical Chemistry Change from Baseline

Note to programmer: Please use the shell from Table 2.6 and include only Planned Relative Time after Baseline.

GlaxoSmithKline  
Example : LB1  
Protocol : 204847  
Population : Safety

Page 1 of n

Table 2.8  
Summary of Haematology Values

Note to programmer: Please use the shell from Table 2.6.

GlaxoSmithKline  
Example : LB1  
Protocol : 204847  
Population : Safety

Page 1 of n

Table 2.9  
Summary of Haematology Change from Baseline

Note to programmer: Please use the shell from Table 2.6 and include only Planned Relative Time after Baseline.

GlaxoSmithKline  
 Example : UR3  
 Protocol : 204847  
 Population : Safety

Table 2.10  
 Summary of Urinalysis Dipstick Results

Study Part: 1

Test	Planned Relative Time	Result	GSK3342830 250 mg (N=xx)	GSK3342830 500 mg (N=xx)	...	Placebo (N=xx)
Urine General Dipstick	Baseline	Positive	xx (xx.x%)	xx (xx.x%)	xx (xx.x%)	xx (xx.x%)
		Negative	xx (xx.x%)	xx (xx.x%)	xx (xx.x%)	xx (xx.x%)
		No Result	xx (xx.x%)	xx (xx.x%)	xx (xx.x%)	xx (xx.x%)
		Not Done	xx (xx.x%)	xx (xx.x%)	xx (xx.x%)	xx (xx.x%)
	Day 2 Follow-up	...	...	...	...	...
	Urine Occult Blood (Dipstick)	Baseline	None	xx (xx.x%)	xx (xx.x%)	xx (xx.x%)
Trace			xx (xx.x%)	xx (xx.x%)	xx (xx.x%)	xx (xx.x%)
1+			xx (xx.x%)	xx (xx.x%)	xx (xx.x%)	xx (xx.x%)
2+			xx (xx.x%)	xx (xx.x%)	xx (xx.x%)	xx (xx.x%)
3+			xx (xx.x%)	xx (xx.x%)	xx (xx.x%)	xx (xx.x%)
4+			xx (xx.x%)	xx (xx.x%)	xx (xx.x%)	xx (xx.x%)

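### Part 2 laboratory tables have no worst post-baseline summary and the laboratory listings start at Grade 3, so a subject stopped on a laboratory limit can drop out of later rows and have confirmatory and recovery values shown nowhere

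*SAP*

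**What the plan says.** SAP section 2.2 defines the Part 2 primary endpoint as "Clinical safety data from AEs, clinical laboratory tests, vital signs (blood pressure, heart rate, temperature, and respiration rate), and 12-lead ECG readings". Protocol 9.4.1 has these summarised as values and change from baseline, says "No inferential hypothesis testing will be performed on the safety variables", and also says that all safety data will be presented in listings.

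The shell for SAP Table 2.6, reused for Tables 2.7-2.9, fixes the rows: "Timepoints for Part 2 are Baseline, Day 2, Day 5, Day 10, Day 15, and Follow-Up". Its footnote excludes unscheduled measurements except when deriving baseline. SAP 10.3.3 gives the general rule, "Unscheduled visits will not be included in summary tables", and sends those visits to listings. For withdrawn subjects, SAP 10.5.1 says "all available planned data will be included in summary tables and figures, unless otherwise specified".

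The stopping rules act on the tabulated variables. Protocol 5.4.2 sets limits for haemoglobin, white cells and platelets. Protocol 5.4.3 includes "Persistent (confirmed on recheck) elevation of serum creatinine (>0.3 mg/dL) without an alternative cause identified". Protocol 5.4 adds: "Any laboratory result that meets the stopping criteria should be repeated once to confirm the value before the subject is withdrawn from the study".

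In SAP Appendix 11, Listings 20-25 show chemistry, haematology and urinalysis only for subjects with a Grade 3 or higher value. A maximum post-dose summary is planned only for QTc (Tables 2.14-2.15). SAP 10.4.1 gives a counting rule for an any-visit post-baseline row and continues: "This will also be applicable to relevant Potential Clinical Importance summary tables". No laboratory shell contains such a row or table.

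**The concern.** Each laboratory row describes the subjects who have a planned value at that visit. A subject taken off because of creatinine or haemoglobin has no assured Day 10 or Day 15 value, so those rows can come to describe the subjects who did not breach a limit. Loss of this kind depends on the outcome. If the drug has an effect, it would fall more on the active arms.

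The listings would normally recover such a subject, but the Grade 3 threshold sits above several stopping limits. A reader of the report could then see that a subject stopped without being able to see how far the value moved, whether the repeat confirmed it, or how it resolved.

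This matters most for haematology, because protocol 4.4 gives haematological safety over 14 days as one of two reasons for the length of Part 2 dosing.

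**Working it through.** **The plan's own figure.** Protocol 9.2.1 gives the only safety probabilities: 26% and 73% for at least one event among 6 active subjects at true rates of 5% and 20%. 1 - 0.95^6 = 26.5% and 1 - 0.80^6 = 73.8%, so both reproduce, the second truncated rather than rounded. The plan states no stopping rate, laboratory SD or expected change. What follows is illustration under assumptions.

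**How often a stop would occur.** Part 2 has about 8 active and 2 placebo subjects per cohort (protocol 4.3). P(at least one stop) = 1 - (1 - p)^n.

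| Assumed rate p | 8 active | 2 placebo |
|---|---|---|
| 5% | 34% | 10% |
| 10% | 57% | 19% |
| 20% | 83% | 36% |

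Equal rates are used here to show the effect of group size only.

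**Effect on a later row.** Let one of 8 stop with change d while the other seven average m. The mean of all eight is (d + 7m)/8, the row shows m, and the gap is (d - m)/8.

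- Creatinine, d = +0.35 and m = +0.05 mg/dL: (0.35 + 0.35)/8 = 0.0875 against 0.05, a shortfall of 0.0375 mg/dL or 43%.
- Creatinine, d from 0.31 to 0.60 and m from 0 to 0.10: gap from 0.21/8 = 0.026 to 0.60/8 = 0.075 mg/dL.
- Haemoglobin, assumed baseline 14 falling to 9.9 g/dL and m = -0.5: (-4.1 - 3.5)/8 = -0.95 against -0.50 g/dL. With baselines of 12.5 to 15.5 and m from 0 to -1.0, the gap is 0.2 to 0.7 g/dL.

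**Dependence on persistence.** These figures assume that d would have been held on treatment. In the first creatinine example, full recovery gives (0 + 0.35)/8 = 0.044 against 0.050, so the sign reverses. The two means agree when the stopped subject keeps +0.05, one seventh of the change.

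**Dependence on timing.** A stop triggered at Day 2 or Day 5 can empty both the Day 10 and Day 15 rows. A Day 10 trigger affects only Day 15, and a Day 15 trigger affects neither.

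**Simulation.** 400,000 subjects were read on Days 2, 5, 10 and 15 and removed after two readings above 0.3 mg/dL at one visit. Assumptions: mean Day 15 change 0.10 to 0.20, between-subject SD 0.10 to 0.15, within-subject SD 0.05 mg/dL.

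| Mean, SD (mg/dL) | Plateau by Day 5: Day 15 row v all dosed | Linear rise to Day 15: Day 15 row v all dosed |
|---|---|---|
| 0.10, 0.10 | 0.094 v 0.100 (6% low) | 0.100 v 0.100 (0%) |
| 0.15, 0.15 | 0.108 v 0.150 (28% low) | 0.144 v 0.150 (4% low) |
| 0.20, 0.15 | 0.139 v 0.200 (31% low) | 0.189 v 0.200 (6% low) |

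In the plateau cases 3% to 25% of subjects had been removed.

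**Listings against stopping limits** (protocol 5.4.2 and 5.4.3; SAP Appendix 7).

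| Limit | Grade at the limit |
|---|---|
| Haemoglobin 99 g/L | Grade 1 (95 to 105) |
| Platelets 99.999 x 10^9/L | Grade 1 (75 to 99.999) |
| White cells 1.0 to 1.999 x 10^9/L | none; the only low grade is below 1 (Grade 4) |
| Creatinine rise just over 0.3 mg/dL | can be far below Grade 3, which starts at 3.1 x ULN |

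None of these would bring the subject into Listings 20-23.

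**The case against.** The strongest reply is that much of this is visible or unsettled, and most of it is right.

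- **Visibility.** Each row prints n beside N, and the minimum and maximum keep a scheduled triggering value. Table 1.2 counts, by treatment, subjects who reached stopping criteria, and Listing 2 names the reason. A clinically significant change is also an adverse event. The subject can return in the Follow-Up row, since that visit applies at early termination. None of these, however, gives the confirmatory or recovery values or the worst change by dose.
- **Removal is not established.** Protocol 5.4 speaks of withdrawal from the study, 5.4.2 and 5.4.3 only of stopping treatment, and the renal row of 4.6.1 of interrupting Part 2 dosing. No text schedules Day 10 or Day 15 visits after a stop, and none rules them out. The loss is therefore possible, not certain.
- **The repeat may not count as unscheduled.** SAP 10.4.1 averages several values at one time point, so a same-visit repeat might enter the row. The SAP does not say.
- **Haematology.** The monkey red-cell fall of 10% to 20% peaked at Week 2. A 20% fall reaches 9.9 g/dL only from 9.9/0.8 = 12.4 g/dL or lower, and normal haemoglobin is an entry condition. A late trigger also empties few rows. A haemoglobin stop of that size is thus not the likeliest case.
- **SAP 10.4.1** is conditional wording. It does not promise a laboratory any-visit row.

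A reader might also infer that vital signs share the gap. They largely do not: Listings 30-31 show all vital signs for subjects with systolic pressure above 160, diastolic above 100 or heart rate above 110, at or inside the limits of protocol 5.4.5.

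**Conclusion.** The gap is real for laboratory data and is one of display. Tables 2.6-2.9 are observed-case by planned visit, have no worst post-baseline row, and sit beside listings whose threshold is above the haemoglobin, platelet and creatinine stopping limits. The confirmatory and recovery values of a stopped subject may therefore appear nowhere, contrary to protocol 9.4.1.

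The size is conditional. With a stop at Day 2 or Day 5 and a change that would have persisted, one subject in 8 moves a later creatinine mean by about 0.03 to 0.08 mg/dL. The simulated Day 15 shortfall is 0% to 31%, with the upper end needing a plateau by Day 5. All of this rests on assumed changes and SDs.

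A reader might infer that the Day 10 and Day 15 changes on active will look smaller. The documents do not support that as a general statement: it depends on when the stop occurs, on persistence, and on whether stopped subjects leave the scheduled visits. Recovery removes or slightly reverses the difference. The correction is worth making because it is cheap and mirrors what the SAP already does for QTc.

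**What to change.** 1. In SAP Tables 2.6-2.9 add a *Worst post-baseline (any visit)* row for value and change, by dose and placebo, using every post-dose value including unscheduled and confirmatory ones.
2. Add the n (%) of dosed subjects meeting each laboratory limit in protocol 5.4.
3. List all laboratory data for any subject who meets a stopping criterion, whatever the grade.
4. Limit the unscheduled-data exclusion in SAP 10.3.3, and the planned-data wording in 10.5.1, to the by-visit rows.
5. Reconcile protocol 5.4, 5.4.2, 5.4.3 and the renal row of 4.6.1 on whether a subject who meets a laboratory limit leaves the study, stops treatment or has dosing interrupted. The tables can then state who is expected at each visit.

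Vital signs need nothing beyond Listings 30-31.

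For items 1-4 the cost is SAP and shell wording, one derived record per parameter and a wider listing, with no new visits, samples or subjects. There is one downside: protocol 7.3.7 has clinically significant abnormal values repeated until they settle, so subjects with a signal contribute more readings and their worst value is slightly more extreme. Keep the by-visit rows alongside for that reason.

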5.4.4. QTc Stopping Criteria

The *same* QT correction formula *must* be used for *each individual subject* to determine eligibility for and discontinuation from the study. This formula may not be changed or substituted once the subject has been enrolled.

- For example, if a subject is eligible for the protocol based on corrected QT interval using Bazett’s formula (QTcB), then QTcB must be used for discontinuation of this individual subject as well.

Once the QT correction formula has been chosen for a subject's eligibility, the *same formula* must continue to be used for that subject *for all QTc data being collected for data analysis*. Safety ECGs and other non-protocol specified ECGs are an exception.

The QTc should be based on single or averaged QTc values of triplicate ECGs obtained over a brief (e.g., 5 to 10 minute) recording period.

Study treatment will be discontinued for a subject who meets either of the following criteria:

- QTc >500 msec OR uncorrected QT >600 msec
- Change from baseline QTc of >60 msec

Withdrawal of subjects will be based on an average QTc value of triplicate ECGs. If an ECG demonstrates a prolonged QT interval, then 2 more ECGs will be obtained over a brief period of time (e.g., 5 to 10 minute) and then the averaged QTc values of the 3 ECGs will be used to determine whether the subject should be discontinued from the study.

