AE = adverse event, BP = blood pressure, ECG = electrocardiogram, HR = heart rate, SAE = serious adverse event.

NOTES:

1. Triplicate 12-lead ECGs will be obtained at least 5 minutes apart within 1 hour before the start of infusion (pre-dose) on Day 1. Single ECGs will be obtained at 0.5, 1, 1.5, 2, 3, 4, 6, and 12 hours after the start of infusion on Day 1 and Day 15, within 1 hour before the start of the morning infusion on Days 2, 3, 4, 5, 6, 7, 8, 9, 10, 11, 12, 13, and 14, and in the morning on Day 16.
2. Vital signs will be measured within 1 hour before the start of infusion (pre-dose) and at 0.5, 1, 1.5, 2, 3, 4, 6, and 12 hours after the start of infusion on Days 1 and 15, within 1 hour before the start of the morning infusion and on Days 2, 3, 4, 5, 6, 7, 8, 9, 10, 11, 12, 13, and 14, and in the morning on Day 16.
3. An aliquot of the urine sample will be collected for neutrophil gelatinase-associated lipocalin (NGAL) and kidney injury molecule 1 (KIM-1). These samples may be analyzed after the end of the study if a clinical signal is detected. Instructions for collection and storage of these urine samples are included in the Study Reference Manual. Hematology assessments on Days 5 and 15 will also include total iron, total iron binding capacity, ferritin, haptoglobin, ceruloplasmin and reticulocytes. The albumin to creatinine ratio will be determined using the first morning void urine on Days 5 and 15. Urinalysis assessments before dosing on Day 15 will also include urine color.
4. GSK3342830 or placebo will be administered as a single IV infusion in the morning on Day 1, TID IV infusions (approximately every 8 hours) on Days 2, 3, 4, 5, 6, 7, 8, 9, 10, 11, 12, 13, and 14, and as a single IV infusion in the morning on Day 15. The planned infusion duration time is 1 hour.

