*Note to Programmer: Continue for all treatments in Part 1, Part 2, and Part 3. Present Part 2 and Part 3 on separate pages. Timepoints for Part 1 and Part 3 are Baseline, Day 1 - 0.5 HR, Day 1 - 1 HR, Day 1 - 1.5 HR, Day 1 - 2 HR, Day 1 - 3 HR, Day 1 - 4 HR, Day 1 - 6 HR, Day 1 - 12 HR, Day 2, Day 3, Follow-Up. Timepoints for Part 2 are Baseline, Day 1 - 0.5 HR, Day 1 - 1 HR, Day 1 - 1.5 HR, Day 1 - 2 HR, Day 1 - 3 HR, Day 1 - 4 HR, Day 1 - 6 HR, Day 1 - 12 HR, Day 2 through Day 14, Day 15 - 0.5 HR, Day 15 - 1 HR, Day 15 - 1.5 HR, Day 15 - 2 HR, Day 15 - 3 HR, Day 15 - 4 HR, Day 15 - 6 HR, Day 15 - 12 HR, Day 16, and Follow-Up. ECG measurements summarized are: Heart Rate (beats/min), PR Interval (msec), QT Interval (msec), QTc Interval (msec), QTcB Interval (msec), QTcF Interval (msec), QRS Duration (msec), QRS Axis (deg), and RR Interval (msec).*

Note: Baseline is defined as the last nonmissing measurement before dosing for the respective treatment period  
 Unscheduled measurements are not included in this summary table except when calculating baseline.

GlaxoSmithKline  
Example : EG2  
Protocol : 204847  
Population : Safety

Page 1 of n

Table 2.13  
Summary of Change from Baseline in ECG Values

Note to programmer: Please use the shell from Table 2.12 and include only Planned Relative Time after Baseline.

GlaxoSmithKline

Example : SAFE\_T1  
Protocol : 204847  
Population : Safety

Page 1 of n

Table 2.14  
Summary of Frequency of Maximum Post-Dose ECG Parameter Corrected QTc Interval

Study Part: 1

	GSK3342830 250 mg (N=XX)	GSK3342830 550 mg (N=XX)	... (N=XX)	Placebo (N=XX)
QTcB (msec)				
n	xx	xx	xx	xx
<=450	xx (xx%)	xx (xx%)	xx (xx%)	xx (xx%)
>450-<=479	xx (xx%)	xx (xx%)	xx (xx%)	xx (xx%)
>=480-<=499	xx (xx%)	xx (xx%)	xx (xx%)	xx (xx%)
>=500	xx (xx%)	xx (xx%)	xx (xx%)	xx (xx%)
QTcF (msec)				
n	xx	xx	xx	xx
<=450	xx (xx%)	xx (xx%)	xx (xx%)	xx (xx%)
>450-<=479	xx (xx%)	xx (xx%)	xx (xx%)	xx (xx%)
>=480-<=499	xx (xx%)	xx (xx%)	xx (xx%)	xx (xx%)
>=500	xx (xx%)	xx (xx%)	xx (xx%)	xx (xx%)

Note to Programmer: Continue for all treatments in Part 1, Part 2, and Part 3. Present Part 2 and Part 3 on separate pages.

GlaxoSmithKline

Example : SAFE\_T1  
Protocol : 204847  
Population : Safety

Page 1 of n

Table 2.15  
Summary of Frequency of Maximum Change from Baseline for ECG Parameter Corrected QTc Interval

Study Part: 1

	GSK3342830 250 mg (N=XX)	GSK3342830 550 mg (N=XX)	... (N=XX)	Placebo (N=XX)
QTcB (msec)				
n	xx	xx	xx	xx

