<=30	xx (xx%)	xx (xx%)	xx (xx%)	xx (xx%)
>30-<=59	xx (xx%)	xx (xx%)	xx (xx%)	xx (xx%)
>=60	xx (xx%)	xx (xx%)	xx (xx%)	xx (xx%)
QTcF (msec)				
n	xx	xx	xx	xx
<=30	xx (xx%)	xx (xx%)	xx (xx%)	xx (xx%)
>30-<=59	xx (xx%)	xx (xx%)	xx (xx%)	xx (xx%)
>=60	xx (xx%)	xx (xx%)	xx (xx%)	xx (xx%)

*Note to Programmer: Continue for all treatments in Part 1, Part 2, and Part 3. Present Part 2 and Part 3 on separate pages.*

Note: Baseline is defined as the last nonmissing measurement before dosing for the respective treatment period.  
Unscheduled measurements are not included in this summary table except when calculating baseline.

GlaxoSmithKline  
 Example : VS1  
 Protocol : 204847  
 Population : Safety

Table 2.16  
 Summary of Vital Signs

Study Part: 1

Vital Sign	Group	N	Planned Relative Time	n	Mean	SD	Median	Min.	Max.
XXXXXXXX (XXX)	GSK3342830 250 mg	XXX	Baseline	xx	xx.x	xx.xx	xx	xx	xx
			Day 1 - 0.5 HR	xx	xx.x	xx.xx	xx	xx	xx
			...						
			Follow-Up	xx	xx.x	xx.xx	xx	xx	xx
XXXXXXXX (XXX)	GSK3342830 500 mg	XXX	Baseline	xx	xx.x	xx.xx	xx	xx	xx
			...						
XXXXXXXX (XXX)	...	XXX	Baseline	xx	xx.x	xx.xx	xx	xx	xx
			...						

*Note to Programmer: Continue for all treatments in Part 1, Part 2, and Part 3. Present Part 2 and Part 3 on separate pages. Timepoints for Part 1 and Part 3 are Baseline, Day 1 - 0.5 HR, Day 1 - 1 HR, Day 1 - 1.5 HR, Day 1 - 2 HR, Day 1 - 3 HR, Day 1 - 4 HR, Day 1 - 6 HR, Day 1 - 12 HR, Day 2, Day 3, Follow-Up. Timepoints for Part 2 are Baseline, Day 1 - 0.5 HR, Day 1 - 1 HR, Day 1 - 1.5 HR, Day 1 - 2 HR, Day 1 - 3 HR, Day 1 - 4 HR, Day 1 - 6 HR, Day 1 - 12 HR, Day 2 through Day 14, Day 15 - 0.5 HR, Day 15 - 1 HR, Day 15 - 1.5 HR, Day 15 - 2 HR, Day 15 - 3 HR, Day 15 - 4 HR, Day 15 - 6 HR, Day 15 - 12 HR, Day 16, and Follow-Up. Vital sign measurements summarized are: Systolic Blood Pressure (mmHg), Diastolic Blood Pressure (mmHg), Oral Temperature (C), and Pulse Rate (beats per min).*

Note: Baseline is defined as the last nonmissing measurement before dosing.  
 Unscheduled measurements are not included in this summary table except when calculating baseline.

GlaxoSmithKline  
Example : VS1  
Protocol : 204847  
Population : Safety

Page 1 of n

Table 2.17  
Summary of Change from Baseline in Vital Signs

Note to programmer: Please use the shell from Table 2.14 and include only Planned Relative Time after Baseline.

GlaxoSmithKline  
 Example : PK01  
 Protocol : 204847  
 Population : PK

Table 3.01  

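### Table 2.15 reports a maximum QTc change but excludes unscheduled post-dose ECGs, so its outlier counts can be too low; Table 2.14 arguably falls under the same rule

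*SAP*

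**What the plan says.** Two SAP tables count QTc outliers by subject: Table 2.14, "Summary of Frequency of Maximum Post-Dose ECG Parameter Corrected QTc Interval", and Table 2.15, "Summary of Frequency of Maximum Change from Baseline for ECG Parameter Corrected QTc Interval".

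- The footnote to the Table 2.15 shell reads "Unscheduled measurements are not included in this summary table except when calculating baseline". The Table 2.14 shell has no footnote on the subject.
- SAP 10.3.3 has a general rule, "Unscheduled visits will not be included in summary tables", followed later by "All unscheduled visits will be included in listings".
- Protocol 5.4.4 states "If an ECG demonstrates a prolonged QT interval, then 2 more ECGs will be obtained over a brief period of time", and bases withdrawal on the average of the three. The two extra ECGs do not appear in the Time and Events tables.
- In Part 2, the Time and Events notes (Protocol 7.1, Table 5, note 1) schedule eight ECGs from 0.5 to 12 hours after the start of infusion on Days 1 and 15. On each of Days 2 to 14 the only scheduled ECG is "within 1 hour before the start of the morning infusion".
- SAP 10.3.2.1 and 10.4.1 average replicate measurements at one time point.
- The Table 2.15 bands are ≤30, >30 to ≤59 and ≥60 msec. The Table 2.14 bands are ≤450, >450 to ≤479, ≥480 to ≤499 and ≥500 msec. The cut-offs match SAP Appendix 6.

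**The concern.** Leaving unscheduled readings out of by-visit means is ordinary practice, because those tables describe a nominal time. A table of each subject's maximum is different. The largest value over a subset of ECGs can equal the largest over all of them or fall below it, but cannot exceed it. Compared with a maximum over all individual post-dose readings, the footnote can only lower the counts or leave them unchanged. It is also asymmetric, since unscheduled readings may define baseline but not the peak.

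Unscheduled ECGs are not a random sample. They tend to be taken because something prompted them. ECG readings are part of the primary safety endpoint, no safety hypothesis is tested, and comparison with placebo is descriptive (Protocol 9.1). Tables 2.14 and 2.15 are the summaries in which a reader would look for a QTc signal by dose.

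**Working it through.** The plan gives no figure for this point to reproduce, so the check sets the rules side by side and counts from the schedule.

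**1. Which table is covered.** Table 2.15 is covered by its own footnote, which refers to measurements. Table 2.14 is covered only if the 10.3.3 rule on unscheduled visits is read to include single unscheduled ECGs.

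**2. Part 2 schedule, per subject.**
- Infusions: 1 (Day 1) + 13 × 3 (Days 2 to 14) + 1 (Day 15) = 41.
- Infusions with a scheduled ECG near the end of infusion: 2 (Days 1 and 15). Without one: 41 − 2 = 39, and 39/41 = 95%.
- Scheduled ECG time points after the first dose: 8 + 13 + 8 + 1 (Day 16) + 1 (Follow-up) = 31.
- Of these, those 0.5 to 2 hours after the start of an infusion: 4 × 2 = 8, all on Day 1 or Day 15.

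An ECG prompted by symptoms after an infusion on Days 2 to 14 is therefore unscheduled, unless it falls in the next morning's pre-dose window. These counts show where unscheduled ECGs could arise. They do not say how many will be taken.

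**3. Confirmatory ECGs.** The documents contain no QTc data, so these changes from baseline (msec) are assumed. They are classified under three possible handling rules with the current Table 2.15 bands.

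| Scheduled; confirmatory | Scheduled only | Mean of three | Maximum of all |
|---|---|---|---|
| 58; 63, 66 | 58: >30 to ≤59 | 187/3 = 62.3: ≥60 | 66: ≥60 |
| 62; 64, 70 | 62: ≥60 | 196/3 = 65.3: ≥60 | 70: ≥60 |
| 61; 57, 60 | 61: ≥60 | 178/3 = 59.3: no band | 61: ≥60 |

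The handling rule changes the result in the first and third cases and not in the second. In the third, averaging lowers the value, so the choice does not always act in one direction. A similar case for absolute QTc (also assumed) is a scheduled 495 with confirmatory 506 and 508. The mean is 1509/3 = 503, above the 500 msec stopping limit. If the two extra ECGs are dropped, Table 2.14 shows 480 to 499. If they are averaged in, it shows ≥500.

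**4. Gaps between bands.** The Day 1 pre-dose ECG is triplicate and is averaged for baseline, while post-dose ECGs are single. Changes in thirds of a msec are therefore expected. With an assumed baseline of 400.33 and a post-dose value of 460, the change is 59.67, which fits no band. The absolute bands have the same gaps at 479 to 480 and 499 to 500. Those matter only if a post-dose value is averaged or derived by formula, for example (479 + 480 + 480)/3 = 479.67.

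**5. Weight of one subject.** Protocol 4.3 plans about 6 active subjects per Part 1 cohort and about 8 per cohort in Parts 2 and 3. One subject is 1/6 = 16.7% or 1/8 = 12.5% of a column.

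**The case against.** Scheduled-only summaries are a convention, and this SAP applies it to ECG and vital-sign tables alike. It has a real merit: a subject with extra ECGs has more chances of an extreme value, and equal sampling avoids that. This stands as a cost of the fix, but it does not make a maximum over selected readings the subject's maximum.

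The values are not lost from the report. SAP 10.3.3 keeps unscheduled readings in listings. Listings 28 and 29 cover ECG values of potential clinical importance, with Appendix 6 thresholds that include QTc above 450 and an increase of 60 msec or more. Table 1.2 counts subjects withdrawn on protocol-defined stopping criteria. With cohorts this small, the listings can be read subject by subject. That limits the harm but does not correct the counts.

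Three stronger readings are tempting, and the documents do not support them:

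- A reader might infer that the confirmatory ECGs are dropped. The SAP does not say so. They are taken within minutes of the triggering ECG, and 10.3.2.1 and 10.4.1 could lead to their being averaged into that time point, which would match the quantity used in 5.4.4. A scheduled triggering ECG stays in the table either way. What is supported is an ambiguity.
- A reader might take 39 of 41 (95%) as the share of readings excluded. It describes the ECG schedule. If no ECG is taken after those infusions, nothing is excluded. Time points added by Note to File (Protocol 7) could also count as planned. Parts 1 and 3 have scheduled ECGs throughout the first 12 hours and at 24 and 48 hours.
- A reader might infer that the bands hide stopping cases because they differ from the >60 and >500 limits. Bands of ≥60 and ≥500 contain every tabulated value above those limits.

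**Conclusion.** The point holds in limited form. As written, Table 2.15 does not report each subject's maximum change when a higher unscheduled post-dose reading exists. Table 2.14 arguably has the same limitation, depending on how broadly 10.3.3 is read. The clearest exposed case is an unscheduled ECG after an infusion on Part 2 Days 2 to 14. The treatment of confirmatory ECGs is unspecified and can change a subject's band.

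The number of affected readings cannot be estimated from the documents. A count changes only when the excluded reading falls in a higher band, and each such subject moves that band by about 12.5 to 16.7 percentage points in an active cohort of planned size. The band examples rest on assumed QTc values. The 59 to 60 msec gap follows directly from the triplicate baseline and is an editorial defect. The issue concerns the accuracy of two summary tables. It does not show that a stopping event would go unrecorded.

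**What to change.** In the shells for Tables 2.14 and 2.15:

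- State that the maximum is taken over all post-dose ECGs, scheduled and unscheduled, and replace the present Table 2.15 footnote accordingly. Add the exception to SAP 10.3.3.
- State how confirmatory ECGs enter. One option is to use the triplicate average of 5.4.4 as the value for that assessment, which keeps the table consistent with the stopping decision.
- Footnote the number of post-dose ECGs per subject, so that unequal sampling is visible.
- Close the gaps without moving the top cut-offs, in line with Appendix 6: ≤30, >30 to <60, ≥60 for change; ≤450, >450 to <480, ≥480 to <500, ≥500 for absolute QTc. Edit Appendix 6 to match. Moving the top change band to >60 would conflict with the Appendix 6 flag at ≥60.

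Keep the by-visit ECG tables scheduled-only. The cost is SAP wording and some programming, with no change to data collection. The downside is that subjects with extra ECGs have more chances of an extreme value. The footnote discloses this but does not remove it.
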